10.2.3.4 Vital Signs

Vital signs, including pulse rate, sitting SBP/DBP, and body temperature, will be collected at screening (V1) and at each study visit. Vital signs will be recorded after the patient has rested in the sitting position for 5 minutes. (See additional exclusion criteria for SBP/DBP screenings in [Section 7.3.1](#) and assessments in [Table 10-1](#)).

CONFIDENTIAL

Blood pressure measurements are to be taken in the same arm for the duration of the study. Body weight (without shoes) will be recorded at screening and V4/ET, and height (without shoes) will be recorded at screening only.

Start and stop dates of last menstrual cycle for all females of childbearing potential will be recorded at screening and at each study visit.

Vital sign measurements will be repeated if clinically significant per the Investigator's judgment or if machine/equipment errors occur. Out-of-range blood pressure, pulse rate, and body temperature measurements will be repeated at the Investigator's discretion. Any confirmed clinically significant vital sign measurement in the Investigator's opinion must be recorded as medical history or an AE, as applicable.

10.2.3.5 Twelve-Lead Electrocardiogram

A 12-lead resting ECG will be performed at screening (V1), and at every study visit. Each ECG will be reviewed by the Investigator. Tracings will be printed, signed, and dated by the Investigator and kept in the patient's file. The overall interpretation and determination of the clinical relevance of ECG findings will be the responsibility of the Investigator and will be recorded in the patient's eCRF.

10.2.3.6 Adverse Events

Adverse Event Definition

An AE is defined as any untoward medical occurrence in a clinical study patient administered a study medication and which does not necessarily have a causal relationship with this treatment. A TEAE is an AE with a start date on or after the initial dose of study medication and up to 5 days after the last dose of study medication. An AE can therefore be any unfavorable and unintended sign (including an abnormal laboratory finding), symptom, or disease temporally associated with the use of the study medication, whether or not related to the study medication. This includes an exacerbation of pre-existing conditions or events, intercurrent illnesses, drug interaction, or the significant worsening of the indication under investigation that is not recorded elsewhere in the eCRF. Anticipated fluctuations of pre-existing conditions, including the disease under study, that do not represent a clinically significant exacerbation or worsening need not be considered AEs. **Migraine headaches will not be captured as AEs.** Migraine headaches will be captured by the patient in the eDiary provided to them.

For the purpose of the site's data collection responsibilities, any untoward event that started or worsened after the informed consent form (ICF) was signed until the final end-of-study visit (inclusive) is to be considered an AE.

It is the responsibility of the Investigator to document all AEs that occur during the study. Adverse events will be elicited by asking the patient a non-leading question, for example, "Have you experienced any new or changed symptoms since we last asked/since your last visit?" Adverse events should be reported on the appropriate page of the eCRF.

CONFIDENTIAL

Assessment of Severity

Each AE will be assigned a category by the Investigator as follows:

Mild	An AE that is easily tolerated by the patient, causes minimal discomfort, and does not interfere with everyday activities.
Moderate	An AE that is sufficiently discomforting to interfere with normal everyday activities; intervention may be needed.
Severe	An AE that prevents normal everyday activities; treatment or other intervention usually needed.

If there is a change in severity of an AE, it must be recorded as a separate event.

Assessment of Causality

Every effort will be made by the Investigator to assess the relationship of the AE, if any, to the study medication. Causality should be assessed using the categories presented in the following table:

Not Related	The event is clearly due to extraneous causes (e.g., diseases, environment), which should be specified if known; or the event is most likely produced by other factors such as the patient's clinical state, therapeutic interventions, or concomitant therapy and does not follow a known response pattern to the study medication.
Possibly Related	The event is temporally related to study medication use but can be explained by another etiology. Information on the effect of study product withdrawal may be lacking.
Probably Related	The event is temporally related to study medication use and is consistent with known effects of the study medication and/or improves upon withdrawal of the study medication.
Definitely Related	The event follows a reasonable temporal sequence from the time of study medication administration and/or follows a known response pattern to the study medication and could not have been produced by other factors such as the patient's clinical state, therapeutic intervention, or concomitant therapy and either occurs immediately following study medication administration or improves on stopping the medication or there is a positive reaction at the application site.

Action Taken

The Investigator will report the action taken in the appropriate section of the eCRF, as follows:

- Dose not changed
- Drug interrupted
- Drug withdrawn
- Not applicable
- Unknown

Follow-up of Adverse Events

The Investigator should follow up on patients with AEs until the events are resolved or until, in the opinion of the Investigator, the events have stabilized or are determined to be chronic. Details of AE resolution must be documented in the eCRF. Patients who

CONFIDENTIAL

have ongoing AEs at the time of study completion or ET should be followed up for 30 days after receiving the last dose of study medication or until the events resolve, are stabilized, or determined to be chronic, whichever occurs first.

Documentation and Reporting of Adverse Events

Adverse events will be reported and documented in accordance with the procedures outlined in this section. Adverse events will be reported from the time of informed consent through V4/ET and documented on the relevant eCRF pages. The following data should be documented for each AE:

- Description of the symptom event
- Classification of "serious" or "not serious"
- Severity
- Date of first occurrence and date of resolution (if applicable)
- Action taken
- Causal relationship
- Outcome of event (unknown, recovered, not yet recovered, recovered with sequelae, death [with date and cause reported]).

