⁷ At screening, patients with a history of hypertension that is uncontrolled (i.e., SBP > 140 mmHg and/or DBP > 90 mmHg), whether on treatment or not, will be excluded. Patients who had high or uncontrolled BPs in the past and are currently controlled with given therapies would be eligible for this study. Independent of past history, if a patient has a sustained resting SBP > 140 mmHg and/or DBP > 90 mmHg at V1 or V2, they should be excluded. Any patient without a known history of hypertension that presents at screening with SBP > 140 mmHg and/or DBP > 90 mmHg should be excluded if the BP reading is due to suspected hypertension or another pathological condition, not if due to a transient fluctuation, based on the Investigator's evaluation. If the Investigator believes the BP is falsely elevated, they should repeat the assessment 2 to 3 times with the patient in a semi-reclined position in a quiet room. Patients with persistent elevations, despite repeat assessments, should be excluded and referred to an appropriate healthcare provider for further assessment.

⁸ Serum pregnancy test will be performed at screening (V1) for all female patients of childbearing potential (or at any other time during the study if needed to confirm a suspected pregnancy from a positive urine pregnancy test).

⁹ Urine pregnancy tests will be performed at all study visits after screening for all female patients of childbearing potential.

¹⁰ Patients will be instructed by the study site staff on the proper administration of study medication to ensure compliance. Written instructions for use of the study medication will be distributed to Investigator sites, and patients should be confirmed to have, or be provided with, the instructions every time study medication is dispensed.

¹¹ Unused study medication, including empty study medication containers, should be returned by patients. Unused study medication should not be redispensed.

¹² When the patient experiences a migraine episode, they should contact the site within 24 hours of treating with study medication to schedule their next visit. The eDiary will be used to record all migraine attacks treated with study medication during the study period.

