10.2.3.7 Serious Adverse Events

Serious Adverse Event Definition

An SAE is any untoward medical occurrence or effect that, at any dose:

- Results in death.
- Is life-threatening. An AE is life-threatening if the patient is at immediate risk of death from the event as it occurs (i.e., it does not include a reaction that might have caused death if it had occurred in a more serious form).
- Requires or prolongs inpatient hospitalization. Complications occurring during hospitalization are AEs and are SAEs if they cause prolongation of the current hospitalization. Hospitalization for elective treatment of a pre-existing non-worsening condition is not, however, considered an AE. The details of such hospitalizations must be recorded on the medical history or physical examination page of the eCRF.
- Results in persistent or significant disability/incapacity. An AE is incapacitating or disabling if it results in a substantial or permanent disruption of the patient's ability to carry out normal life functions.
- Is a congenital anomaly/birth defect.

In addition, medical and scientific judgment is required to decide if prompt notification is required in situations other than those defined for SAEs above (i.e., any event that the Investigator regards as serious that did not strictly meet the criteria above but that may have jeopardized the patient or required intervention to prevent one of the outcomes listed above, or that would suggest any significant hazard, contraindication, side effect, or precaution that may be associated with the use of the study medication).

Reporting of Serious Adverse Events

Patients should report all SAEs that occur during the clinical study, or within 30 days of receiving the last dose of study medication, to the Investigator. It is the responsibility of the Investigator to follow the procedures described below, whether or not the SAE is considered to be related to the study medication.

CONFIDENTIAL

At the first occurrence of an SAE, the Investigator should complete an SAE report and notify the Sponsor within 24 hours of occurrence of the SAE. An SAE report consists of the SAE form, the concomitant medication form, and any available supporting documentation (e.g., hospital discharge summary). A copy of the SAE form must be emailed **within 24 hours** to the attention of Dr. [REDACTED] at:

[name] Inc.

[REDACTED]

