11.6.6 Safety Analysis

All AEs will be coded using the latest version of the Medical Dictionary for Regulatory Activities (MedDRA) version 19.0 or higher. A TEAE is an AE with a start date on or after the initial dose of study medication and up to 5 days after the last dose of study medication. Only TEAEs will be included in summary tables. Migraine headaches will not be captured as AEs. Migraine headaches will be captured by the patient in the eDiary provided to them at screening. The information will then be entered into the appropriate eCRF page.

The incidence of all TEAEs will be tabulated by treatment received. These TEAEs will be classified by system organ class (SOC) and preferred term (PT). For incidence reporting, if a patient reported more than one AE that was coded to the same SOC or PT, the patient will be counted only once for that specific SOC or PT.

An overview of AEs, which includes patient incidence of TEAEs, headache or migraine-related TEAEs, study medication-related TEAEs, and SAEs, will be presented. The patient incidence of TEAEs, headache- or migraine-related TEAEs, study medication-related TEAEs, and SAEs will be summarized by SOC and PT.

CONFIDENTIAL

Treatment-emergent adverse events will also be summarized in a table by severity. For TEAEs presented by severity, the worst severity during the study will be presented for each patient, SOC, and PT.

Treatment-emergent adverse events will also be summarized in a table by relationship to study medication. For TEAEs presented by relationship to study medication, the strongest relationship to study medication during the study will be presented for each patient, SOC, and PT.

All AEs will also be presented in a by-patient data listing.

All prior and concomitant medications will be classified using the Anatomical Therapeutic Chemical (ATC) classification and preferred drug names from the World Health Organization Drug Dictionary (WHO-DD), version March 2016 or later. Medications will be considered concomitant if they were taken at any time between the date of first dose and the date of last dose of study medication, inclusive. Medications will be considered as prior if stopped before the date of first dose of study medication during the DB1 treatment period.

Prior and concomitant medications will be summarized in separate tables by ATC level 2 and preferred drug name for the safety population.

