9.3. ADVERSE EVENTS

All AEs will be coded using the Medical Dictionary for Regulatory Activities (MedDRA; version 19.0 or higher). Migraine headaches will not be captured as AEs. Migraine headaches will be captured by the subject in the eDiary provided to them, and the information will be entered into the appropriate eCRF page.

All AEs will be listed by subject. The following listings of AEs will be provided:

- All AEs
- Study medication-related AEs
- Serious adverse events (SAEs)
- AEs leading to death
- Adverse events leading to study medication termination

Statistical Analysis Plan

Final V1.0

[name], Ltd.
Protocol #DFN-02-CD-012
INC Research #1007752

Only TEAEs will be included in summary tables. Summaries for AEs will be presented for the SS, SS1, and SS2. An overall summary table of TEAEs will be produced for the following categories:

- Any TEAE
- Study medication-related TEAEs
- Serious TEAEs
- TEAEs leading to study medication termination
- TEAEs leading to death

All TEAEs will be classified by system organ class (SOC) and preferred term (PT). Frequency count and the number of unique subjects of a TEAE will be tabulated by treatment(s) received. For the number of unique subjects reporting, if a subject reported more than one AE that was coded to the same SOC or PT, the subject will be counted only once for that specific SOC or PT.

The following summaries of TEAEs will also be provided:

- TEAEs by SOC and PT
- Study-medication related TEAEs by SOC and PT
- Serious TEAEs by SOC and PT
- TEAEs by maximum severity (mild, moderate, severe or missing) by SOC and PT
- TEAEs by strongest causality relationship (not related, possibly related, probably related, definitely related or missing) by SOC and PT

For TEAEs presented by relationship to study treatment(s), the strongest relationship to study treatment(s) during the study will be presented for each subject if coded to the same SOC or PT. For TEAEs presented by severity, the worst severity during the study will be presented for each subject if coded to the same SOC or PT. TEAEs with missing causality will be counted as related. TEAEs with missing severity will be counted as severe. The same will be true in the individual summaries.

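### The rule that migraine headaches are not AEs has no exception for serious ones and contradicts the protocol's own SAE definition

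*Protocol*

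**What the plan says.** **Exclusion.** Protocol 10.2.3.6 says in bold that "Migraine headaches will not be captured as AEs" and names the replacement route: "Migraine headaches will be captured by the patient in the eDiary provided to them". Protocol 11.6.6 and SAP 9.3 repeat the exclusion and add where the data go; in the SAP's words, "Migraine headaches will be captured by the subject in the eDiary provided to them, and the information will be entered into the appropriate eCRF page". No exception for seriousness appears in any of the three.

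**AE definition.** The same section 10.2.3.6 includes among AEs "the significant worsening of the indication under investigation that is not recorded elsewhere in the eCRF". It exempts expected fluctuations of the disease only when they are not a clinically significant worsening. It also tells sites to treat as an AE anything untoward that begins or gets worse between consent and the final visit.

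**AE record.** 10.2.3.6 lists seriousness and causal relationship among the data to document for each AE.

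**SAE definition.** Protocol 10.2.3.7 covers any untoward occurrence that meets a listed criterion, one of which is "Requires or prolongs inpatient hospitalization". Its one hospitalisation exclusion is elective treatment of a pre-existing condition that is not worsening. Notification is on a separate SAE form within 24 hours.

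**Diary scope.** Footnote 12 to Protocol Table 10-1 says "The eDiary will be used to record all migraine attacks treated with study medication during the study period". Protocol 10.2.1.4.1 sets the same limit for attack date and time, and adds non-study medication used for migraine. The Protocol Synopsis and SAP 3.4 instead describe recording each migraine attack.

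**Analysis.** Protocol 11.6.6 states: "An overview of AEs, which includes patient incidence of TEAEs, headache or migraine-related TEAEs, study medication-related TEAEs, and SAEs, will be presented". The TEAE categories in SAP 9.3 contain no headache- or migraine-related group.

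**The concern.** A disease-under-study exclusion is common in AE collection, because routine attacks are efficacy data. It normally stops at the point where an event becomes serious. Here the text does not say where it stops. An investigator whose patient is admitted for a migraine finds one section that bars the event from the AE record and another that makes it an SAE, with no order of precedence.

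At stake is consistent capture of serious events in the condition being treated, including any that follow study drug. The SAP's SAE listing is one of its AE listings, and its summary tables take TEAEs only. An event with no AE record has no stated path into either.

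**Working it through.** No arithmetic applies. The check sets the rules side by side for the kinds of attack that matter.

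| Attack during a double-blind period | Bold exclusion (10.2.3.6, 11.6.6, SAP 9.3) | Worsening clause (10.2.3.6) | Begins-or-worsens rule (10.2.3.6) | SAE definition (10.2.3.7) |
|---|---|---|---|---|
| Hospitalised, treated with study drug | Not an AE | Can lapse: diary data go to an eCRF page | AE | SAE |
| Hospitalised, not treated with study drug, narrow diary scope | Not an AE | AE if a significant worsening, since no attack record is required elsewhere | AE | SAE |
| Hospitalised, not treated with study drug, wide diary scope | Not an AE | Can lapse, as in the first row | AE | SAE |
| Significantly worse, no seriousness criterion met | Not an AE | Depends on whether it is in the diary | AE | Not an SAE |

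1. **The conflict is in the text.** In each of the first three rows the exclusion says not an AE and 10.2.3.7 says SAE. The result does not depend on which diary scope is right.

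2. **The worsening clause does not settle it.** It holds only while the worsening is not on another eCRF page. Protocol 11.6.6 and SAP 9.3 put diary migraines on such a page. Where the clause does hold, it still faces the bold sentence.

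3. **The effect on outputs.** If a site follows the exclusion, the event has no AE record, so no seriousness or causality entry. It is then absent from the SAE listing in SAP 9.3 and, if it began within the TEAE window of up to 5 days after the last dose, from the TEAE tables. If a site follows 10.2.3.7, the event is reported.

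4. **The diary as substitute.** The documents give two scopes. The SAP has both: SAP 3.4 says each attack, while footnote 12 to SAP Table 1 says attacks treated with study medication. On either scope, the visible items in Protocol Table 10-2 and 10.2.1.4.1 cover pain, symptoms, disability, satisfaction and medication. None records seriousness or causality, and both are investigator judgements. Some diary items are blacked out, so this statement covers the visible ones only.

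5. **The planned summary.** The exclusion leaves the protocol's headache- or migraine-related TEAE summary without migraine events. SAP 9.3 and the SAP's index of tables omit the summary. SAP Section 11 lists changes to Sections 4.3, 5.3, 5.4, 7.1, 7.2, 8.1.1, 8.2, 8.2.1, 8.2.9, 8.2.11 and 8.2.12, but nothing for 9.3.

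**The case against.** The strongest reply is that SAE reporting does not run through the AE record. Section 10.2.3.7 is freestanding, has its own form and 24-hour route, and asks investigators to use judgement about other events they regard as serious. Read on its own, it makes a hospitalised migraine reportable. That stands. A reader might infer that the protocol forbids SAE reporting of migraine; it does not. What remains is that 10.2.3.7 and the exclusion point in opposite directions and neither yields to the other.

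Three further inferences also go too far:

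- **That a worsened migraine escapes SAE reporting.** Worsening alone is not a seriousness criterion in 10.2.3.7. Without one, the gap concerns AE capture only.
- **That migraine can under no reading be an AE.** The worsening clause, the limit on the fluctuation exemption and the begins-or-worsens rule all say otherwise.
- **That the diary holds nothing but attacks treated with study drug.** The Synopsis and SAP 3.4 are wider. Protocol 10.2.1.4.1 adds other migraine medication and at least one screening attack. Protocol 10.1.1 has staff contact patients who report no attack for 2 to 3 weeks. Visits 3 and 4 also include AE and medication review. The accurate statement is that the scope is inconsistent.

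On the missing summary, Protocol 11.1 lets the SAP supersede the protocol, and a headache coded as an AE would still appear by system organ class and preferred term. The omission is therefore a minor documentation point.

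**Conclusion.** The point holds as a contradiction that needs reconciling. Protocol 10.2.3.6 and 11.6.6 and SAP 9.3 exclude migraine from AE capture without a seriousness exception. Protocol 10.2.3.7, and other text within 10.2.3.6, say the opposite for a serious attack and for some worsened ones. The consequence is possible site-to-site difference in whether a serious migraine enters the AE record, the SAE listing and the TEAE tables.

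No size can be attached: the documents give no rate of serious migraine, and a count of routine attacks without a diary record would say nothing about serious ones. The conclusion assumes that some sites would take the bold sentence literally. The documents neither show nor rule this out.

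**What to change.** 1. In Protocol 10.2.3.6 and 11.6.6 and in SAP 9.3, state that the exclusion does not apply to a migraine or headache meeting any criterion in 10.2.3.7. Such an event is recorded as an AE and reported as an SAE, whether or not it was treated with study medication or entered in the eDiary.
2. In the same edit, say how the exclusion and the worsening clause in 10.2.3.6 apply to a significantly worsened attack that meets no seriousness criterion.
3. Use one diary scope in the Synopsis, Table 10-1 footnote 12, Protocol 10.2.1.4.1, SAP 3.4 and SAP Table 1 footnote 12.
4. Either restore the headache- or migraine-related TEAE summary in SAP 9.3 and its table index, or list its removal in SAP Section 11.

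The cost is a short text change in both documents, a memo to sites and a few extra SAE forms. The primary analysis and sample size are unaffected.
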